10.2 Planned recruitment rate

The target number of participants will be 40 that will be recruited over 12 months, therefore our target recruitment rate will be 3 – 4 participants per month.

10.3 Statistical analysis plan

10.3.1 Summary of baseline data and flow of patients

The variables to be used to assess baseline comparability of the randomised groups will include:

- 1) Age
- 2) Sex
- 3) Lung function
- 4) Number of exacerbations in the previous year
- 5) GOLD COPD category

A consort flow diagram will be produced

10.3.2 Primary outcome analysis

The primary endpoint (median sputum glucose in treated versus non-treated participants) will be analysed using a Mann-Whitney test. The post-treatment sputum glucose will also be compared with baseline glucose using Wilcoxon matched-pairs test. Similar methods will be used to analyse the secondary endpoints.

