3.3 Outcome measures/endpoints

3.4 Primary endpoint/outcome

The median concentration of glucose in sputum in COPD patients after 3 months treatment with metformin compared with 3 months of placebo.

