4 TRIAL DESIGN

The proposed study will be a randomised, double-blinded, placebo-controlled, cross-over study of metformin in patients between the ages of 40 and 75 with a confirmed diagnosis of COPD. It will be an exploratory pilot trial, to gather preliminary information on the effects of metformin on sputum glucose and the feasibility of conducting a full-scale trial.

All subjects will have clinical assessments and blood, airway samples (nasal SAM and sputum) collected at baseline prior to the treatment phase. Clinical assessments will include lung function (FEV₁ and FVC), quality of life and symptom questionnaires (St George's Respiratory Questionnaire, COPD assessment test). Subjects will then either be commenced on metformin or placebo for a period of 3 months and blood, sputum and nasal samples collected at monthly intervals. Following a 2 week washout period the subjects will crossover to the other study arm for another 3 months and repeat samples collected.

Primary Outcome

The primary outcome will be sputum glucose measured using an enzymatic assay (AmplexRed® – ThermoFisher) after 3 months treatment with metformin. There is currently no data on which to base a power calculation and therefore this pilot study will assess what the size of any effect of metformin is in COPD subjects and thereby provide data that can be used to power any future, larger clinical trials.

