10 STATISTICS AND DATA ANALYSIS

10.1 Sample size calculation

The primary outcome will be change in sputum glucose from baseline after treatment with metformin, measured using an enzymatic assay (AmplexRed®). The median glucose concentration in COPD subjects measured in our previous study was 1,007 µM (SD 733µM). Metformin reduced airway glucose by c.30% in studies carried out in mice. Therefore to detect a similar effect in humans would require 30 subjects with 90% power at 5% significance. We aim to recruit 40 subjects to account for possible withdrawals.

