10.3.3 Secondary outcome analysis

Same as for primary outcome

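### The primary metformin-placebo comparison is an unpaired Mann-Whitney test in a cross-over trial, so it ignores the pairing and loses power if a participant's two values correlate positively

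*Combined protocol and SAP*

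**What the plan says.** Section 4 sets the design: "The proposed study will be a randomised, double-blinded, placebo-controlled, cross-over study of metformin". On the second period it adds: "Following a 2 week washout period the subjects will crossover to the other study arm for another 3 months and repeat samples collected". The schedule in Appendix 2 has a sputum sample at baseline and at months 1, 2 and 3 of each arm.

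Section 3.4 defines the primary endpoint: "The median concentration of glucose in sputum in COPD patients after 3 months treatment with metformin compared with 3 months of placebo".

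Section 10.3.2 gives the analysis: "The primary endpoint (median sputum glucose in treated versus non-treated participants) will be analysed using a Mann-Whitney test". It then adds: "The post-treatment sputum glucose will also be compared with baseline glucose using Wilcoxon matched-pairs test". For the secondary endpoints it says "Similar methods will be used to analyse the secondary endpoints", and section 10.3.3 says only "Same as for primary outcome".

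Section 10.1 justifies the size: "Therefore to detect a similar effect in humans would require 30 subjects with 90% power at 5% significance". It plans to recruit 40 to allow for withdrawals. Section 10 mentions no period, sequence or within-participant correlation.

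**The concern.** A participant who completes both periods is in the treated group and in the untreated group. The two sets of values therefore come from the same people, and the independence that the Mann-Whitney test needs fails by design. The Wilcoxon matched-pairs test does not repair this, because a change from baseline is not the randomised contrast between metformin and placebo. Neither test allows for a period effect.

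Two kinder readings were considered. A rank-sum test is valid in a cross-over when it compares each person's period difference between the two sequences, but section 10.3.2 describes treated against untreated values and names no sequence. A comparison restricted to the first period would also be valid, but it would discard half the data, and nothing in the text supports it.

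The choice does not change the two observed medians. It makes the p-value and the precision wrong for the design. Section 4 intends the trial to estimate the size of effect for powering later studies, and section 2 says a positive result would justify a trial with exacerbations as the primary outcome. A real effect missed here could end that programme, and the same methods carry over to every secondary endpoint.

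**Working it through.** **Inputs.** Section 10.1 gives a median of 1,007 µM, SD 733 µM, a reduction of about 30%, 5% significance, 90% power and 30 subjects. *Assumed*: two-sided testing (sidedness is not stated), and a within-participant correlation ρ, which the documents do not give, varied from 0 to 0.8.

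- Difference: 0.30 × 1,007 = 302.1 µM, or ln(0.7) = −0.357 on the log scale.
- Log-SD of a log-normal variable with this median and SD: u(u − 1) = (733/1,007)² with u = exp(σ²). This gives u = 1.383 and σ = 0.569.
- z-values: 1.960 + 1.2816 = 3.2415.

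**Step 1: the plan's figure of 30.**

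- Unpaired, normal: 2 × (3.2415 × 733 / 302.1)² = 124 per treatment.
- Unpaired, log-normal: 2 × (3.2415 × 0.569 / 0.357)² = 54 per treatment.
- Unpaired, one-sided: 101 and 44 per treatment.
- Paired, taking 733 as the SD of differences: (3.2415 × 733 / 302.1)² = 62.
- Paired, two-sided, solving for 30: needs ρ ≈ 0.76 on the raw scale or ρ ≈ 0.44 on the log scale.

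The figure is not reproduced from the printed inputs. It can be reached with a paired comparison and an unstated correlation. It does not correspond to the unpaired test in 10.3.2.

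**Step 2: type I error.** The true variance of the mean difference is 2σ²(1 − ρ)/n, but an unpaired test works with 2σ²/n. A nominal 5% test then has true error of about 2 × [1 − Φ(1.96/√(1 − ρ))]: 5.0, 1.9, 0.56 and 0.03% at ρ = 0, 0.3, 0.5 and 0.7. Simulation of the Mann-Whitney test itself (table) agrees closely, apart from the far tail, where this formula is rough.

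**Step 3: power.** 40,000 simulated trials per setting, 30 completers, 30% reduction. Signed-rank is on metformin-placebo differences (log differences in the log-normal model). Period-adjusted is a rank-sum test of period differences between two sequences of 15. All entries except ρ are percentages.

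| ρ | Mann-Whitney type I error | Log-normal: Mann-Whitney | Log-normal: signed-rank | Log-normal: period-adjusted | Normal: Mann-Whitney | Normal: signed-rank | Normal: period-adjusted |
|---|---|---|---|---|---|---|---|
| 0 | 4.8 | 64 | 63 | 61 | 33 | 32 | 31 |
| 0.3 | 2.0 | 66 | 78 | 77 | 30 | 44 | 42 |
| 0.5 | 0.7 | 68 | 90 | 89 | 28 | 57 | 55 |
| 0.7 | 0.1 | 73 | 99 | 98 | 24 | 79 | 77 |
| 0.8 | 0.01 | 77 | >99 | >99 | 21 | 92 | 91 |

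The log-normal model is the more credible one. The normal model puts Φ(−1,007/733) = 8.5% of placebo values and Φ(−704.9/733) = 16.8% of metformin values below zero.

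Loss against signed-rank: none at ρ = 0; 78 − 66 = 12 to 44 − 30 = 14 points at 0.3; 90 − 68 = 22 to 57 − 28 = 29 points at 0.5.

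**Step 4: sensitivity (log-normal).**

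- Signed-rank on raw differences, 30 completers: 61, 75, 88 and 98% at ρ = 0, 0.3, 0.5 and 0.7. The loss is then 75 − 66 = 9 points at 0.3 and 88 − 68 = 20 at 0.5.
- All 40 complete: Mann-Whitney 77, 80, 84 and 90% against signed-rank on log differences 76, 89, 96 and >99%. The loss is 9, 12 and about 9 points at 0.3, 0.5 and 0.7.
- ρ = −0.3: Mann-Whitney errs the other way, with type I error of about 8 to 9%.

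A separate simulation with 10,000 trials per setting gave the same Mann-Whitney type I errors and power to within simulation error. Its signed-rank results, on raw differences, also agreed.

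**The case against.** The strongest counter-argument is that section 10.1 calls the primary outcome a change from baseline, and Appendix 2 has a baseline sputum sample in each period. Subtracting each period's own baseline largely removes the participant effect. Simulated on that reading (log-normal, equal correlation between visits, 30 completers, ρ = 0.3, 0.5 and 0.7), Mann-Whitney had type I error of 4.5, 4.9 and 4.9% and power of 41, 52 and 73%, against 39, 50 and 72% for signed-rank on the same changes. The pairing loss disappears. However, sections 3.4, 3.7 and 10.3.2 all use the month-3 value. That power is also well below the 78, 90 and 99% from a paired comparison of month-3 values. If one shared baseline were used instead, two changes have covariance σ²(1 − ρ) and variance 2σ²(1 − ρ), so they correlate at 0.5 and type I error is again about 0.8%. What stands is that sections 10.1 and 3.4 need reconciling.

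Other points stand as limits:

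- Part of the gain in the log-normal columns comes from the log scale, which the plan does not name, and the gap narrows with 40 completers.
- The shortfall from 90% is partly a sample-size problem. With 30 completers the paired test also misses 90% below ρ = 0.5 (log-normal, log differences) and at ρ = 0.7 and below (normal).
- Section 7.3 specifies simple randomisation, so the sequences may be unequal. A period effect would then shift the raw medians, and the 15:15 split in the table is not guaranteed.
- For positive ρ the error is conservative, and this is an exploratory pilot. That softens the consequence, but section 10.1 still claims 90% power.

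**Conclusion.** The concern holds. The named test is wrong for a cross-over, and no other section supplies a paired comparison of metformin with placebo. The direction is certain for positive correlation: type I error below the nominal level and lost power. The size depends on an unknown ρ. With 30 completers the loss against signed-rank on log differences (log-normal model) or raw differences (normal model) is nil at ρ = 0, about 12 to 14 points at 0.3 and more than 20 from 0.5 upwards. It is smaller under the variants in step 4. With 30 completers the Mann-Whitney test does not reach 90% power at any ρ from 0 to 0.8 under either model; its highest value is about 77%. This should be corrected before unblinding.

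**What to change.** Rewrite section 10.3.2 so that the primary analysis is a within-participant comparison of month-3 sputum glucose on metformin and placebo, adjusted for period. Name one of these as primary:

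- **(a)** Take each participant's log glucose in period 1 minus period 2 and compare these differences between the two sequences with a rank-sum test. With treatment effect τ and period effect π, the sequences centre on π + τ and π − τ, so half the Hodges-Lehmann shift estimates τ. Back-transform it to a metformin/placebo ratio with a 95% CI.
- **(b)** Fit a linear mixed model to log glucose with fixed effects for treatment, period and sequence and a random participant effect. Report the ratio with a 95% CI.

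Keep the two treatment medians as descriptive summaries. Label the comparison with baseline as supportive. Carry the within-participant structure into section 10.3.3. Bring section 10.1 into line with section 3.4 on whether the outcome is the month-3 value or a change.

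The cost is the wording of 10.3.2 and 10.3.3, plus that one clarification in 10.1. No extra patients, visits or samples are needed, because the data are already scheduled.

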10.3.3 Secondary outcome analysis

Same as for primary outcome

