Therefore this study was the first to link elevated glucose in the lung to bacterial infection in COPD. Therefore reducing airway glucose has the potential to inhibit bacterial growth in COPD patients. One potential approach is to use the anti-diabetic drug metformin. In animal studies we have demonstrated that metformin decreases airway glucose and bacterial colonisation (4). The aim of the proposed study is to investigate whether metformin can achieve the same effects in COPD patients. Metformin is safe, cheap, does not cause hypoglycaemia and has been extensively used in COPD patients with diabetes with an excellent safety record (5). The primary aim of this study will be to evaluate the effects of metformin on lung glucose in COPD patients. If the study successfully demonstrates that metformin reduces airway glucose it will provide the data needed to justify a clinical trial of metformin with exacerbations as the primary outcome.

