3.5 Secondary endpoints/outcomes

These will also be assessed in COPD patients after 3 months treatment with metformin compared with placebo.

- 1) Median glucose concentration measured in nasal SAM strips
- 2) Bacterial infection (sputum semi-quantitative culture)
- 3) Inflammatory markers measured in sputum
- 4) Number of COPD exacerbations
- 5) Quality of life/symptom scores
- 6) Lung function measured using spirometry

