6.1 Inclusion criteria

Age 40-85 years

A clinical diagnosis of COPD confirmed with spirometry (Post-bronchodilator FEV₁/FVC <70%)

A smoking history of at least 15 pack years

Absence of infection for at least 8 weeks prior to study entry

No use of antibiotics and oral corticosteroids at least 8 weeks prior to study entry

Able to understand and consent to the study procedures

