7 TRIAL PROCEDURES

All subjects will have clinical assessments and blood, airway samples (nasal SAM and sputum) collected at baseline prior to the treatment phase. Clinical assessments will include lung function (FEV₁ and FVC), quality of life and symptom questionnaires (St George's Respiratory Questionnaire, COPD assessment test). Women of childbearing potential will only be included after a confirmed menstrual period and a negative highly sensitive urine pregnancy test. Subjects will then either be commenced on metformin or placebo for a period of 3 months and blood, sputum and nasal samples collected at monthly intervals. Following a 2 week washout period the subjects will crossover to the other study arm for another 3 months and repeat samples collected.

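### COPD exacerbations, a sparse count seen on both treatments in each participant, are sent to an unpaired rank test, with no rate, rate ratio or confidence interval planned

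*Combined protocol and SAP*

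**What the plan says.** Section 3.5 lists "Number of COPD exacerbations" as the fourth secondary endpoint, assessed after 3 months of metformin compared with placebo. Its whole planned analysis is in sections 10.3.2 and 10.3.3. The first says "The primary endpoint (median sputum glucose in treated versus non-treated participants) will be analysed using a Mann-Whitney test", adds a Wilcoxon matched-pairs comparison of post-treatment with baseline glucose, and closes with "Similar methods will be used to analyse the secondary endpoints". The second says "Same as for primary outcome".

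The design is a cross-over: "Following a 2 week washout period the subjects will crossover to the other study arm for another 3 months" (section 7). Exacerbation data are collected at each monthly visit (section 7.7). The only earlier exacerbation count that the plan names is "Number of exacerbations in the previous year", listed in section 10.3.1 for baseline comparability. Entry requires "Absence of infection for at least 8 weeks prior to study entry" (section 6.1).

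On the next step, section 2 says that if metformin is shown to reduce airway glucose, "it will provide the data needed to justify a clinical trial of metformin with exacerbations as the primary outcome".

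**The concern.** The plan carries a method chosen for a continuous concentration over to a low count. Three things do not fit.

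- **Pairing.** The two counts come from the same person, but Mann-Whitney treats them as coming from different people.
- **Output.** A rank test gives a p-value. It gives no rate per treatment, no rate ratio and no interval. Changing to a paired rank test would repair the pairing but not this.
- **Baseline comparison.** A Wilcoxon comparison with baseline needs a count over a comparable baseline window. A previous-year count covers 12 months against 3 on treatment. A 3-month count before entry, if one were built, would be low by selection, because 8 of about 13 weeks must be free of infection.

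At stake is what the pilot can report on the outcome that the later trial would use. Planning such a trial calls for a control rate and some idea of the effect with its uncertainty.

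**Working it through.** **Inputs.** From the documents: 3 months (0.25 year) on each treatment; 30 subjects needed and 40 recruited (section 10.1). The documents give no exacerbation rate, so annual rates of 1 to 3 are assumed, with counts either Poisson or negative binomial (dispersion k = 0.5 or 1). The plan states no figure of its own for exacerbations, so there is none to reproduce.

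**Step 1: how sparse is the count?** With annual rate r, the mean per period is m = 0.25r. The chance of no event is P0 = exp(−m) for Poisson, or (1 + km)^(−1/k) for negative binomial. At 1 per year P0 is 0.78 to 0.80, so about four counts in five are zero. The population median over 3 months is 0 whenever P0 exceeds 0.5, which means an annual rate below 4 × ln 2 = 2.77 (Poisson), 3.31 (k = 0.5) or 4.0 (k = 1).

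**Step 2: when are both sample medians 0?** With n even, the sample median is exactly 0 if at least n/2 + 1 counts are zero, which is a binomial tail in P0. As an approximation, the tail is squared for the two treatments (no treatment effect, treatments taken as independent).

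Example with n = 30, Poisson, 1.5 per year: m = 0.375, P0 = 0.687, P(at least 16 of 30 are zero) = 0.975, and 0.975² = 0.951. At 2 per year: m = 0.5, P0 = 0.607, tail 0.843, and 0.843² = 0.711.

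| Assumed rate per year | P(both medians 0), n = 30 to 40, across the three distributions |
|---|---|
| 1 | at least 0.999 |
| 1.5 | 0.95 to 0.996 |
| 2 | 0.71 to 0.96 |
| 2.5 | 0.34 to 0.83 |
| 3 | 0.09 to 0.60 |

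A simulation that lets each person's two counts share a gamma frailty (variance 0.5, assumed rate ratio 0.7, 3,000 runs) gives, for n = 30 and 40: 1.00 and 1.00 at 1 per year, 0.99 and 1.00 at 1.5, 0.91 and 0.94 at 2, and 0.50 and 0.56 at 3.

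**Step 3: what would a within-person rate ratio look like?** With complete periods, and leaving the period term aside, the conditional Poisson rate ratio is the ratio of total events, and the person's own rate cancels. With A events on placebo and C on metformin, the standard error of the log ratio is √(1/A + 1/C). The 95% interval is the estimate divided and multiplied by F = exp(1.96 × √(1/A + 1/C)).

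| n | Rate per year | Assumed rate ratio | Expected A | Expected C | F |
|---|---|---|---|---|---|
| 30 | 1 | 0.7 | 7.5 | 5.25 | 3.05 |
| 30 | 1 | 0.5 | 7.5 | 3.75 | 3.45 |
| 40 | 2 | 0.7 | 20 | 14 | 1.98 |
| 40 | 2 | 0.5 | 20 | 10 | 2.14 |

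Simulated medians of F are slightly larger at the sparse end because event numbers vary: about 3.3 (ratio 0.7) and 3.6 (ratio 0.5) at n = 30 and 1 per year, against 2.0 at n = 40, 2 per year and ratio 0.7. The working range is therefore about 2 to 3.6. The ratio cannot be computed if one treatment has no events. With a Poisson total of 3.75 expected events that chance is exp(−3.75) = 0.02, and with 5.25 it is exp(−5.25) = 0.005.

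**The case against.** The other side has a good deal right.

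- **The rate is unknown.** Section 1 calls exacerbations frequent, and section 6.1 sets no cap on exacerbation history. A reader might infer that the comparison must come out as 0 against 0. The documents do not support that: it depends on the rate, and at 3 per year it may well not happen.
- **Medians are not stated for this endpoint.** Section 3.5 writes median for nasal glucose and only a number for exacerbations. A median summary is inferred from section 10.3.3. Mann-Whitney works on ranks and still returns a p-value when both medians are 0.
- **Power is not the argument.** A reader might expect the count model to detect more. At 2 per year, frailty variance 1.5, a halved rate and n = 30, simulated power was 16% for Mann-Whitney, 30% for a paired Wilcoxon test and 28% for a conditional count test. Pairing explains the gap, and the count model adds none.
- **Unequal follow-up.** Section 10.7 restricts analysis to participants with the required drug exposure, so the periods analysed should be about equal as the plan stands. An offset matters only if partial periods are included.
- **The pilot does not promise an exacerbation effect.** Section 2 makes glucose the condition for the next trial, and the remark in section 4 about powering future trials stands under the primary outcome. The data are collected, so a rate ratio would be unplanned, not lost.

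All of this stands. It limits the point but does not answer it: the planned test still ignores the cross-over, the baseline comparison still lacks its input, and no estimate is planned for this endpoint.

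**Conclusion.** The point holds as a cheap improvement, not as a flaw that threatens the trial. That the plan has an unpaired test, no matching baseline count, and no rate, rate ratio or interval follows from the text and needs no assumption. How uninformative a median summary would be does depend on an assumed rate. Both medians are 0 with probability 0.95 or more up to 1.5 per year, 0.71 to 0.96 at 2, and 0.09 to 0.60 at 3, treating the two treatments as independent and equally effective. The interval factor of about 2 to 3.6 assumes 1 to 2 exacerbations per year, 30 to 40 analysed participants, a rate ratio of 0.5 to 0.7, and Poisson variation within each person. Extra within-person variation would widen it.

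**What to change.** For secondary endpoint 4, replace the cross-reference in section 10.3.3 with one sentence. Exacerbation counts will be analysed with a within-participant count model (conditional Poisson, or Poisson with a participant random effect), with treatment and period terms and an offset of log days observed in the period. The report gives the rate on each treatment and the rate ratio with 95% confidence interval, as estimation and not as a test. Drop the comparison with baseline for this endpoint, or define a matching baseline window for it.

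The change needs no new data, visits or participants, and should be made before unblinding. The cost is a wide interval, and a small chance that one treatment has no events and the ratio cannot be estimated.
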